15.2.2. Intercurrent Event Handling and Data Imputation for Secondary Immunogenicity Variable(s)

Missing data will not be replaced.

15.2.3. Analysis of Secondary Immunogenicity Variables

The secondary immunogenicity endpoints will be analyzed as follows:

- MGI and 95% CIs for within participants ratios of the post-dose titer (at 1 month after the RSVPreF3 OA investigational vaccine dose) over the pre-dose titer (at pre-vaccination) for RSV-A neutralizing Ab titers (ED60 and IU/mL)
- MGI and 95% CIs for within participants ratios of the post-dose titer (at 1 month after the RSVPreF3 OA investigational vaccine dose) over the pre-dose titer (at pre-vaccination) for RSV-B neutralizing Ab titers (ED60 and IU/mL)

Missing data will not be replaced. Titers below the assay cut-off will be replaced by half the assay cut-off, titers above the upper limit of quantification (ULOQ) will be replaced by the ULOQ.

15.2.4. Within group assessment

For each group, at each time point that blood samples are collected and for each assay (unless otherwise specified):

- Percentage of participants above pre-defined assay cut-off for GMCs and GMTs and their exact 95% CI will be tabulated.
- GMTs and their 95% CI over time will be tabulated and presented graphically (in log10 scale).
- MGI for within participants ratios of the post-dose GMT or GMC (at 1-month after the RSVPreF3 OA investigational vaccine dose) over the pre-dose titer (at baseline) for RSV-A/RSV-B neutralizing titers/concentrations will be tabulated.
- Antibody titers will be displayed using reverse cumulative curves.
- Percentages of participants with GMFR and 95% CIs for within participants ratios of the post-dose titer (at 1 month after the PCV investigational vaccine dose) over the pre-dose titer (at pre-vaccination) for PCV OP Ab titers for each serotype.
- Percentage of participants and 95% CIs for participants with a 4-fold increase in PCV OP Ab titers from pre-dose titer (at pre-vaccination) to post-dose titer (at 1 month after the PCV investigational vaccine dose) for PCV OP Ab titers for each serotype.
- Percentage of participants and 95% CIs for participants with a 4-fold increase in RSV-A neutralizing Ab titers (ED60 and IU/mL) from pre-dose titer (at pre-vaccination) to post-dose titer (at 1 month after the RSV investigational vaccine dose) for RSV-A neutralizing Ab titers (ED60 and IU/mL).
- Percentage of participants and 95% CIs for participants with a 4-fold increase in RSV-B neutralizing Ab titers (ED60 and IU/mL) from pre-dose titer (at pre-vaccination) to post-dose titer (at 1 month after the RSV investigational vaccine dose) for RSV-B neutralizing Ab titers (ED60 and IU/mL).
- Percentage of participants and 95% CIs for participants with OPA Ab titers \geq LLOQ (pre-defined assay cut-off) at pre-vaccination and/or 1 month post-vaccination (Day 31 for Co-Ad group and Control group) for each serotype.
- The above mentioned descriptive within group immunogenicity analysis will also be generated by age at first vaccination (60-69 YOA, 70-79 YOA, \geq 60 YOA, \geq 65 YOA and \geq 80 YOA years).

Missing results will not be replaced. Titers and concentrations below the assay cut-off will be replaced by half the assay cut-off, titers above the upper limit of quantification (ULOQ) will be replaced by the ULOQ.

Note: For PCV20 summaries, pre-vaccination is at Visit 1 for Co-Ad group and for Control group. For RSV-A and RSV-B neutralizing titer and concentration summaries, pre-vaccination is at Visit 1 for Co-Ad group and at Visit 2 for Control group.

15.2.5. Secondary Immunogenicity Variables

- The secondary immunogenicity endpoints will be repeated by age group at first vaccination (60-69 YOA, 70-79 YOA, ≥60 YOA, ≥65 YOA and ≥ 80 YOA).

[figure not shown]
16. SAFETY OUTCOMES

All outputs for safety outcomes will be based on the ES.

There will be no statistical comparisons between the study intervention groups for safety data.

Secondary Safety Endpoints

- Solicited events
 - Percentage of participants reporting each solicited administration site event (pain, erythema / redness, swelling) with onset within 7 days (i.e., the day of vaccination and 6 subsequent days) following each dose and overall. Percentage of participants reporting each solicited systemic event (fever, headache, fatigue, myalgia, arthralgia) with onset within 7 days (i.e., the day of vaccination and 6 subsequent days) following each dose and overall
- Unsolicited adverse events
 - Percentage of participants reporting unsolicited AE within 30 days (i.e., the day of vaccination and 29 subsequent days) following each dose and overall
- Combined solicited and unsolicited AEs
 - Percentage of participants with combined solicited and unsolicited AEs (any grades, Grade 3, medically attended) during the 4-day (i.e., the day of vaccination and 3 subsequent days), 7-day (i.e., the day of vaccination and 6 subsequent days), and 30-day follow-up period (i.e., the day of vaccination and 29 subsequent days).
- SAEs

- Percentage of participants reporting SAEs after vaccine administration (Day 1) up to End of Study (EoS) (6 months after last vaccination)
- pIMDs
 - Percentage of participants reporting pIMDs after vaccine administration (Day 1) up to EoS (6 months after last vaccination), where pIMDs commence after vaccine administration (Day 1) and are not present prior to vaccine administration or are present prior to vaccine administration and worsened after vaccine administration (Day 1).

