	administered (Co-Ad) or received separately (Control)	YOA	events within 7 days after each vaccine administration		eDiary will be captured	administration site events within 7 days after each vaccine administration (Days 1-7 after each vaccine, PCV20 and RSVPref3 OA) [i.e., date of RSVPref3 OA vaccine administration for Control group becomes Day 1 for recording events within 7 days]).
Secondary	RSVPref3 OA and PCV20 co-administered (Co-Ad) or received separately (Control)	Adults aged \geq 60 YOA	Solicited systemic event within 7 days after each vaccine administration	1. eDiary not completed on each day	1. Missing data won't be imputed. Compliance to eDiary will be captured	Percentage and exact 95% CIs of participants with solicited systemic events within 7 days after each vaccine administration (Days 1-7 after each vaccine, PCV20 and RSVPref3 OA [i.e., date of RSVPref3 OA vaccine administration for Control group becomes Day 1 for recording events within 7 days]).
Secondary	RSVPref3 OA and PCV20 co-administered (Co-Ad) or received separately (Control)	Adults aged \geq 60 YOA	Each unsolicited adverse event within 30 days of each vaccine administration	1. Permanently discontinued from study due to any reasons prior to Day 31	1. Missing data won't be imputed. Summaries will present the actual data	Percentage and exact 95% CIs of participants with unsolicited adverse events within 30 days after each vaccine administration (Days 1-30 after each vaccine, PCV20 and RSVPref3 PA [i.e., date of RSVPref3 OA vaccine administration for

[figure not shown]
CCI

PPD

CCI

						Control group becomes Day 1 for recording events within 30 days])
Secondary	RSVPreF3 OA and PCV20 co-administered (Co-Ad) or received separately (Control)	Adults aged \geq 60 YOA	Each serious adverse event (SAE) within 6 months of last dose of study intervention	1. Permanently discontinued from study due to any reasons prior to end of study	1. Missing data won't be imputed. Summaries will present the actual data	Percentage and exact 95% CIs of participants with SAEs within 6 months after last dose of study intervention (Days 1 to 6 months [i.e., 180-210] after each vaccine [i.e., date of RSVPreF3 OA vaccine administration for Control group becomes Day 1 for recording events within 6 months]).

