5.4. Exposed Set [ES]

All participants in the ENR who received a study intervention. Analysis per group is based on the study intervention administered (i.e., study intervention actually received).

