16.1. Adverse Events

Adverse Events (AEs) will be coded using MedDRA central coding dictionary, version 25.1 or higher. Adverse events will be described using frequency and percentage.

Adverse Events will be grouped by SOC, HLT and PT and summarized by study intervention at time of onset of the AE. The summary tables will present the number and percentage of total participants and number of events, by SOC, HLT, and by PT for each study intervention.

For the summaries of AEs, participants who experience the same AE (in terms of the MedDRA SOC, HLT and PT) more than once will only be counted once for that event in the number of participants but all occurrences of the same event will be counted in the number of events.

Causality, as indicated by the Investigator is classed as “related” and “not related” to RSVPreF3 OA vaccine and to PCV20 vaccine. A “related” AE is defined as an AE with a relationship to study intervention as “related”. If a participant reports the same AE more than once within that SOC / PT, the AE with the worst-case relationship to study intervention will be used in the corresponding relationship summaries for each study intervention.

See [APPENDIX 2](#) for handling of partial dates for AEs.

Summaries of events considered causally related by investigator to study intervention will be reported separately for each study intervention (RSVPreF3 OA and PCV20).

Summaries of events by age group will be summarized by age groups: 60-69 YOA, 70-79 YOA, ≥ 60 YOA, ≥ 65 YOA and ≥ 80 based on age at first vaccination.

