- The number and percentage of participants and doses with at least one administration site event (solicited only), with at least one systemic event (solicited only), with any solicited event during 4-day follow-up period and 7-day follow-up period after vaccination, and also events ongoing at the end of the 7 day follow-up period, will be tabulated with exact 95% CI after each dose and overall, by visit. This summary will be repeated by age group.
- The number and percentage of participants, with exact 95% CIs, reporting each solicited event (administration site and/or systemic) will be summarized separately for any grades, Grade 3 and medically attended events during the 4-day follow-up and the 7-day follow-up period (i.e., the day of vaccination and 6 subsequent days), following each dose and overall dose and overall participant. This summary will be repeated by age group.
- The number and percentage of participants, with exact 95% CIs, reporting administration site solicited events (pain, erythema, swelling) will be summarized separately for any grades, Grade 3 and medically attended

events during the 7-day follow-up period (i.e., the day of vaccination and 6 subsequent days) and 4-day follow-up period following each dose and overall and overall participant. This summary will also be repeated by age group.

- The number and percentage of participants, with exact 95% CIs, reporting systemic solicited events (fever, headache, fatigue, myalgia, arthralgia) will be summarized separately for any grades, Grade 3 and medically attended events during the 30-day follow-up period (i.e., the day of vaccination and 29 subsequent days), 7 day follow-up period and 4-day follow-up period following each dose, overall dose, and overall participant. This summary will also be repeated by age group.
- Duration in days of solicited events will be summarized as follows:

The duration of an event with a start and end date will be the difference between the start and end date plus one day, i.e., an event that starts on 03MAR2018 and ends on 12MAR2018, has a duration of 10 days.

For solicited administration site and systemic events (including grade 3):

- The duration of a solicited AE with at least one day Grade > 0 is defined as End date (CEENDY) – Start date (CESTDY) + 1, with Start date defined as the first day with the symptom and End date defined as the last day with the symptom in or beyond the solicited period.

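### The SAP sets no denominator for solicited-event percentages beyond the Exposed Set; applied literally, dose recipients with no eDiary data count as if event-free

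*SAP*

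**What the plan says.** - **Analysis set.** SAP 16 opens with "All outputs for safety outcomes will be based on the ES" and makes no exception for solicited events. SAP 5.4 defines the set as "All participants in the ENR who received a study intervention", and adds: "Analysis per group is based on the study intervention administered (i.e., study intervention actually received". SAP section 5 has no set restricted to participants with solicited-event data.
- **Percentages.** SAP 16.1 says of AE tables in general: "The summary tables will present the number and percentage of total participants and number of events". SAP 16.1.1 says solicited events "will be tabulated with exact 95% CI after each dose and overall, by visit", and that the number and percentage of participants "reporting each solicited event (administration site and/or systemic) will be summarized separately for any grades, Grade 3 and medically attended events". Neither section says what the percentage is taken over, whether by dose or overall.
- **Missing eDiaries.** For both solicited-event estimands, SAP 2.4 lists as the only intercurrent event "1. eDiary not completed on each day" and handles it with "Missing data won't be imputed. Compliance to eDiary will be captured".
- **Compliance.** SAP 16.1.1.1 does define denominators, but only for eDiary completion tables by group and dose.
- **Missed doses.** Protocol 7.1 and 7.1.1 foresee participants who do not receive every planned dose, including Control participants who may not go on to the RSV vaccine.

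**The concern.** Solicited events are known only through the eDiary. A participant who received a dose and made no entry has an unknown outcome. If the percentage is taken over the whole ES, that person is in the denominator and cannot be in the numerator, so the unknown outcome is treated as no event. SAP 2.4 says such data will not be imputed, so the only stated analysis set and the estimand handling pull in different directions.

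Reactogenicity of the two vaccines given together or separately is part of a secondary objective. SAP 16 plans no statistical comparison of groups for safety, so readers will set the percentages and exact intervals side by side. The shares without data may also differ: Co-Ad has one vaccination visit and one diary period, whereas Control has two, the second depending on a dose that some may not receive. Compliance tables let a reader see a shortfall but do not correct the percentages or their intervals.

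**Working it through.** **1. The plan's own figure.** The plan states no solicited-event percentage and no eDiary non-completion rate, so there is none to reproduce or contradict. The only figure borrowed is group size. Protocol 9.5 and SAP 2.5 give 490 evaluable per group with 10% non-evaluable: 490 / (1 − 0.10) = 544.4, rounded up to 545, and 2 × 545 = 1090, as stated. N = 545 is used below only as an illustrative ES size. The 10% concerns evaluability for immunogenicity; here it merely marks the top of an assumed range for missing eDiaries.

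**2. Formula.** Let N be the dose recipients in the ES, m the share with no eDiary data for that dose, and p the event rate among those with data.

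- Participants with data: n = N(1 − m). Events: X = p × n.
- Over those with data: X / n = p.
- Over the full ES: X / N = p(1 − m).
- Understatement: p − p(1 − m) = p × m.

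Coding the N × m participants without data as no event gives the same X / N, so leaving them in the denominator and imputing no event are arithmetically identical.

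**3. Size over assumed ranges** (percentage points, p × m):

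| p | m = 1% | m = 2% | m = 5% | m = 10% |
|---|---|---|---|---|
| 10% | 0.1 | 0.2 | 0.5 | 1.0 |
| 30% | 0.3 | 0.6 | 1.5 | 3.0 |
| 50% | 0.5 | 1.0 | 2.5 | 5.0 |
| 70% | 0.7 | 1.4 | 3.5 | 7.0 |

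**4. Effect on the exact (Clopper-Pearson) 95% intervals, N = 545:**

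| m | p | Over those with data | Over the full ES |
|---|---|---|---|
| 2% | 50% | 267/534 = 50.0% (45.7–54.3) | 267/545 = 49.0% (44.7–53.3) |
| 5% | 50% | 259/518 = 50.0% (45.6–54.4) | 259/545 = 47.5% (43.3–51.8) |
| 10% | 50% | 245/490 = 50.0% (45.5–54.5) | 245/545 = 45.0% (40.7–49.2) |
| 10% | 70% | 343/490 = 70.0% (65.7–74.0) | 343/545 = 62.9% (58.7–67.0) |

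At m = 2% or 5% the full-ES interval still covers p; at m = 10% in these rows it does not.

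**5. Unequal shares.** If both groups had p = 60%, with m = 3% in Co-Ad and m = 10% at Control dose 2 (all assumed), the full-ES figures would be 0.60 × 0.97 = 58.2% and 0.60 × 0.90 = 54.0%. That is an apparent gap of 4.2 points where none exists. RSV alone would look milder and co-administration relatively worse.

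**6. Control participants who never received the RSV dose.** They belong to the ES through PCV20. However, the ES grouping rule refers to the intervention actually received, SAP 2.4 counts Control's post-RSV window from the RSV vaccination date, and SAP 16.1.1 tabulates by dose. A participant without that dose has no such window. This wording fits a denominator of dose recipients but does not fix one. It also says nothing about recipients with no eDiary entry.

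**The case against.** The best case against the point is that naming an analysis set does not fix the denominator of every percentage. No sentence in the SAP says that a missing eDiary counts as no event, and SAP 2.4 says missing data are not imputed. SAP section 8 refers to output templates that set the content of the tables; these are not among the documents reviewed and may carry the right denominators. A reader might infer that the plan prescribes counting missing eDiaries as event-free. The text does not support that: the gap is an unstated denominator, not a stated wrong one. Nor does it support saying that Control participants who missed the RSV dose definitely stay in that dose's denominator, given step 6.

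Three further objections have weight. The sizes rest wholly on assumed rates. The protocol works to limit missing eDiaries, with frequent site review, online monitoring, pursuit of unreturned diaries and caregiver help, so m may be small. And requiring at least one entry does not settle how unrecorded days in a partly completed diary are treated; it also assumes that participants without entries resemble those with them.

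What remains is that nothing in the supplied text removes dose recipients with no eDiary data from the denominator. A programmer who takes the ES as N follows the only stated basis and produces the result the estimand disclaims.

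**Conclusion.** The point holds as a conditional one. If the ES is used as N for solicited events, percentages are understated by p × m: 0.1 to 7 percentage points for assumed p of 10–70% and m of 1–10%. For uncommon events the effect is at most about 1 point.

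A reader might infer that the understatement flatters co-administration. The documents do not support that. Its direction between groups depends on where data are missing, and dilution at Control dose 2 would work against co-administration. The effect is confined to descriptive secondary safety summaries; no primary non-inferiority analysis and no formal safety test is involved. It should be corrected because the ambiguity is easily removed and these percentages are the reactogenicity result.

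**What to change.** In SAP 16 and 16.1.1:

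- Keep the ES for unsolicited AEs, SAEs and pIMDs.
- For solicited events, set the per-dose denominator to ES participants who received that dose and have at least one Day 1–7 solicited-event eDiary entry for it.
- Define the overall denominator as ES participants with such data for at least one dose.
- Show the number exposed and the number with eDiary data, by group and dose.
- State how partly completed eDiaries are counted.
- Align the two solicited-event estimands in SAP 2.4, and check that the table templates agree.

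The cost is SAP wording and one denominator flag. Denominators become slightly smaller and reported event rates slightly higher. Data collection does not change.

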16.1. Adverse Events

Adverse Events (AEs) will be coded using MedDRA central coding dictionary, version 25.1 or higher. Adverse events will be described using frequency and percentage.

Adverse Events will be grouped by SOC, HLT and PT and summarized by study intervention at time of onset of the AE. The summary tables will present the number and percentage of total participants and number of events, by SOC, HLT, and by PT for each study intervention.

For the summaries of AEs, participants who experience the same AE (in terms of the MedDRA SOC, HLT and PT) more than once will only be counted once for that event in the number of participants but all occurrences of the same event will be counted in the number of events.

Causality, as indicated by the Investigator is classed as “related” and “not related” to RSVPreF3 OA vaccine and to PCV20 vaccine. A “related” AE is defined as an AE with a relationship to study intervention as “related”. If a participant reports the same AE more than once within that SOC / PT, the AE with the worst-case relationship to study intervention will be used in the corresponding relationship summaries for each study intervention.

See [APPENDIX 2](#) for handling of partial dates for AEs.

Summaries of events considered causally related by investigator to study intervention will be reported separately for each study intervention (RSVPreF3 OA and PCV20).

Summaries of events by age group will be summarized by age groups: 60-69 YOA, 70-79 YOA, ≥ 60 YOA, ≥ 65 YOA and ≥ 80 based on age at first vaccination.

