^a Visit 3 should preferably be done on site but if deemed necessary (during special circumstances such as the COVID-19 pandemic), this study visit can be replaced by a home visit conducted by authorized staff. Any information from the participant required according to study procedures and not collected during the home visit can be obtained by means of a phone call conducted by the site staff.

^b Six months after last vaccination. For this contact, multiple formats (e.g., email, text message, fax, or phone call) can be proposed by the study site.

^c Visit window shown in [Table 4](#)

^d Sample collected at Day 1 will be used as baseline for PCV20 antibody titers.

^e Sample collected at Day 31 will be used for the post-vaccination PCV20 vaccine-related testing. This sample will also be used as baseline for the RSV vaccination in the Control group.

^f Sample collected at Day 61 will be used for the post-vaccination RSV vaccine-related testing.

^g The route for measuring body temperature can be oral or axillary. Fever is defined as temperature $\geq 38.0^{\circ}\text{C}/100.4^{\circ}\text{F}$, regardless of the location of measurement.

^h Designated site staff should review the eDiary frequently during the active event collection period to assess participant/caregiver compliance and monitor reported events.

ⁱ SAEs related to study participation, or to a concurrent GSK medication/vaccine should be collected from the time of consent obtained (prior to study vaccine administration) up to EoS.

Table 3 Interval Between Study Visits (Co-ad Group)

Interval	Planned visit interval	Allowed interval (Visit window)
Visit 1 (Day 1/study intervention administration) → Visit 2 (Day 31)	30 days	30-42 days
Visit 1 → phone contact	180 days	180-210 days

Table 4 Interval Between Study Visits (Control Group)

Interval	Planned visit interval	Allowed interval (Visit window)
Visit 1 (Day 1/study intervention administration) → Visit 2 (Day 31)	30 days	30-42 days
Visit 2 (Day 31/study intervention administration) → Visit 3 (Day 61)	30 days	30-42 days
Visit 2 → phone contact	180 days	180-210 days

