6.1. Reference Start Date and Study Day

Study Day will be calculated from the reference start date and will be used to show start / stop day of assessments and events. It will appear in every listing where an assessment date or event date appears.

Reference start date is defined as Day 1 for the day of each vaccination, where study day is the number of days following the latest vaccination.

- If the date of the event is on or after the reference date, then:
$$\text{Study Day} = (\text{date of event} - \text{reference date}) + 1.$$
- If the date of the event is prior to the reference date, then:
$$\text{Study Day} = (\text{date of event} - \text{reference date}).$$

In the situation where the event date is partial or missing, Study Day, and any corresponding durations will appear partial or missing in the listings unless otherwise stated.

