6.4. Windowing Conventions

Allowed time window for each visit will be performed as mentioned in “Schedule of Activities”, section 1.3 of protocol. Intervals between study visits are included in Table C: (Co-Ad group) and Table D (Control group).

Table C: Intervals between Study Visits (Co-Ad Group)

Interval	Planned visit interval	Allowed interval (Visit window)
Visit 1 (Day 1 / study intervention administration) → Visit 2 (Day 31)	30 days	30-42 days
Visit 1 → phone contact	180 days	180-210 days

Table D: Intervals between Study Visits (Control Group)

Interval	Planned visit interval	Allowed interval (Visit window)
Visit 1 (Day 1 / study intervention administration) → Visit 2 (Day 31)	30 days	30-42 days
Visit 2 (Day 31 / study intervention administration) → Visit 3 (Day 61)	30 days	30-42 days
Visit 2 → phone contact	180 days	180-210 days

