16.1.4. Serious Adverse Events

Analysis of serious adverse events (SAEs) from first vaccination (Visit 1, Day 1) up to 6 months post-last vaccination, the reporting period will start at vaccination and will end at approximately 6 months post last vaccination received for Co-Ad group participants (i.e., 180-210 days post last-dose) and approximately 6 months post last vaccination received for Control group participants. SAEs will be summarized by MedDRA SOC, HLT and PT.

SAEs will be summarized and listed as:

- The number and percentage of participants, with exact 95% CIs, with at least one report of SAE with onset after each vaccine administration up to study end (i.e., 6 months post-last vaccination). This summary will be repeated for: This summary will be repeated for:
 - Considered Causally related by investigator SAEs
 - Fatal SAEs
- All SAEs will be included in a listing.
- All SAEs leading to study discontinuation or vaccine discontinuation at any point from first vaccination up to study end will be included in a listing and a tabulated listing.

16.1.5. pIMDs

For analysis of pIMDs from first vaccination (Visit 1, Day 1) up to 6 months post-last vaccination, the reporting period will start at vaccination and will end at 6 months post-last vaccination (i.e., day of last vaccination+[180-210]). pIMDs will be summarized by MedDRA SOC, HLT and PT.

pIMDs will be summarized and listed as follows:

- The number and percentage of participants, with exact 95% CIs, with at least one report of pIMD (all pIMDs, considered causally related by investigator separately) with onset after each vaccine administration up to study end (i.e., 6 months post-last vaccination) will be summarized.

- All pIMDs will also be described in detail in a listing and in a tabulated listing of pIMDs leading to discontinuation of study will be provided. Classification by new onset vs exacerbations of pIMDs will also be presented.
- The number and percentage of participants, with exact 95% CIs, with at least one report of neurological demyelinating disorder with onset within 30 days of any dose will be summarized. This summary will be repeated for serious neurological demyelinating disorder with onset after each vaccine administration up to study end.

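### The SAP gives conflicting attribution rules and windows for SAEs and pIMDs in the Control group, and none of them yields comparable crude percentages

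*SAP*

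**What the plan says.** Five places in the SAP bear on how a Control-group SAE or pIMD is counted.

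- **SAP 16.1**, the parent section for all adverse events: "Adverse Events will be grouped by SOC, HLT and PT and summarized by study intervention at time of onset of the AE". It continues: "The summary tables will present the number and percentage of total participants and number of events, by SOC, HLT, and by PT for each study" …; the tables are thus described per intervention. The denominator is participants, and no person-time is mentioned.
- **SAP 16.1.4**, SAEs: participants "with at least one report of SAE with onset after each vaccine administration up to study end". **SAP 16.1.5**, pIMDs: "with onset after each vaccine administration up to study end (i.e., 6 months post-last vaccination) will be summarized". Neither ends the first vaccine's window when the second is given.
- **SAP 2.4**, estimand table: both rows use a window of 180-210 days after each vaccine, and in Control the RSVPreF3 OA date becomes Day 1.
- **SAP 16**, endpoint list: both endpoints are per participant, from Day 1 to end of study.
- **SAP Appendix 1**: the only output groups named are Co-Ad and Control.

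SAP 6.1 adds a listing convention: "Reference start date is defined as Day 1 for the day of each vaccination, where study day is the number of days following the latest" …, so in Control the count restarts at the RSV dose.

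The Control timings are in SAP 6.4, Table D: "Visit 1 (Day 1 / study intervention administration) → Visit 2 (Day 31) 30 days 30-42 days" and "Visit 2 → phone contact 180 days 180-210 days". Protocol 1.3, Table 4 agrees. Protocol 8.0 allows a further 30 days before the Control RSV dose in exceptional situations.

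**The concern.** In Co-Ad both vaccines are given on one day, so all these rules amount to one window. In Control they diverge, because the second vaccine comes 30-42 days after the first and most of the follow-up comes after the second.

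A crude percentage of participants with an event grows with the time observed. If two columns cover different lengths of time, they differ even when neither vaccine has any effect. The rule also decides which vaccine a Control event is shown against. This matters for a secondary objective that describes the safety of the two vaccines given together or alone, and pIMDs are the only adverse events of special interest in the study (Protocol 10.3.3). A programmer could follow the SAP and build any of several different tables.

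**Working it through.** **Inputs** (SAP 6.4, Tables C and D; Protocol 8.0)

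- Control, PCV20 dose to RSV dose: 30 days planned, 30-42 allowed; 42 + 30 = 72 with the exceptional extension.
- Control, RSV dose to final contact: 180 days planned, 180-210 allowed.
- Co-Ad, both doses to final contact: 180 days planned, 180-210 allowed.

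**The plan's own figures.** SAP 3.1 gives total participation of 6 months (Co-Ad) and 7 months (Control). With 30-day months, 180/30 = 6 and (30 + 180)/30 = 7. Both reproduce.

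**Window lengths under each reading**

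| Reading | First window | Second window | Ratio |
|---|---|---|---|
| Intervention at onset (16.1) | Control PCV20: 30-42 days | Control RSV: 180-210 days | RSV/PCV20: 180/42 = 4.3 to 210/30 = 7.0; planned 180/30 = 6.0; with extension 180/72 = 2.5 |
| Each vaccine to study end (16.1.4, 16.1.5 read literally) | Control PCV20: 30 + 180 = 210 to 42 + 210 = 252 days | Control RSV: 180-210 days | PCV20/RSV: (30 + 210)/210 = 1.14 to (42 + 180)/180 = 1.23; planned 210/180 = 1.17 |
| Whole study by group (16, Appendix 1) | Control: 210-252 days | Co-Ad: 180-210 days | Control/Co-Ad: planned 210/180 = 1.17 |

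Under the second reading, every Control event after Visit 2 follows both vaccines and so counts under both.

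The estimand table can be taken in two ways:

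- If each vaccine has its own 180-210 days, the windows are equal in length but overlap. At planned times, 180 - 30 = 150 of the 180 PCV20 days fall after the RSV dose.
- If Control simply restarts at the RSV dose, the 30-42 days after PCV20 alone drop out. That disagrees with an endpoint that starts on Day 1.

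**What this does to percentages.** The documents give no event rates, so this is an illustration. Assume a constant hazard, no vaccine effect and a risk p over 180 days. The percentage with an event by day d is 1 - (1 - p)^(d/180).

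| Assumed p | 30 days | 42 days | 180 days |
|---|---|---|---|
| 2% | 0.34% | 0.47% | 2.0% |
| 5% | 0.85% | 1.19% | 5.0% |
| 10% | 1.74% | 2.43% | 10.0% |

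Under the 16.1 reading with p = 5%, PCV20 alone would show 0.85-1.19% against 5.0% for RSV alone and for Co-Ad. At group level, Control would show 1 - 0.95^(210/180) = 5.8% against 5.0% for Co-Ad.

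**The case against.** The strongest reply is that nothing in the SAP says SAEs or pIMDs go only to the vaccine received last.

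- The SAE and pIMD text has its own wording, with no cut-off at the next dose.
- The endpoint list and Appendix 1 point to Co-Ad and Control columns. Elsewhere, for instance in the estimand table and in SAP 9.1, study intervention means the group.
- Repeats by dose and by visit are specified for unsolicited AEs (SAP 16.1.2) but not for SAEs or pIMDs.
- The table templates are not part of the documents.
- SAP 16 plans no statistical comparison of safety between groups.

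All of this stands. A reader might infer that last-vaccine columns are already settled, so that PCV20 alone is bound to look several-fold safer. The documents do not support that: the 4.3- to 7.0-fold ratio applies to one reading only. A reader might also infer that any Control pIMD arising more than about six weeks after PCV20 will be charged to RSVPreF3 OA. The documents do not support that either. SAP 16.1.5 has no such cut-off, and SAP 16.1 reports related events separately for each vaccine, so a late event judged related to PCV20 would appear under PCV20 there.

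The reply does not remove the conflict. The phrase about time of onset in SAP 16.1 does nothing if columns are randomised groups, because a group never changes. The same section names the study interventions as RSVPreF3 OA and PCV20 when it describes causality summaries.

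Part of the remedy already exists. Unsolicited AEs include serious ones (Protocol 10.3.1) and are tabulated over 30 days by dose, but there SAEs are mixed with non-serious events. The 30-day SAE tables in SAP 16.1.3 are for any dose. SAEs and pIMDs are listed, but study day counts from the latest vaccination only.

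**Conclusion.** The concern holds as an unresolved conflict in the SAP; it does not show that a biased table has been specified. The general rule, the SAE and pIMD text, the estimand table and the endpoint list with its output groups do not agree on the window or the attribution for Control. No reading gives crude percentages that can be compared at face value: the windows differ in length, overlap across vaccines, or leave out the period after PCV20 alone.

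The size depends on the reading: 4.3- to 7.0-fold under SAP 16.1 (6.0 as planned, as low as 2.5 with the extension), about 1.2-fold the other way under the literal SAP 16.1.4 and 16.1.5 wording, and about 1.17-fold between groups. These are ratios of window length. Percentages follow them closely only if the hazard is roughly constant and events are fairly rare, and both are assumptions.

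No confirmatory conclusion changes. What is exposed is the descriptive reporting of a secondary safety objective.

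**What to change.** State one rule, in the same terms, in SAP 16.1, 16.1.4, 16.1.5 and the estimand table:

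1. Report SAEs and pIMDs from Day 1 to end of study by group (Co-Ad and Control), with exposure-adjusted rates beside the percentages.
2. Show per-vaccine SAE and pIMD percentages only for Day 1-30 after each dose. The shortest allowed interval between Control doses is 30 days, and Day 1-30 means the vaccination day plus 29 more, so these windows do not overlap.
3. List later Control events with days since each dose, without assigning them to one vaccine.

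The cost is SAP wording and table shells. Dose and event dates are already collected. The downside is a few extra table columns and sparse 30-day counts. In the same edit, the pIMD row of the estimand table needs correcting, because its summary column refers to SAEs.
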